### 3.3. C.4 Assessments :

These will include eye tracking of attention allocation during GC-MRT, self-ratings, clinician ratings (by an independent evaluator blind to GC-MRT dose assignment and scheduling of GC-MRT sessions), computer-based behavioral tasks, and MRI. Attention allocation will be assessed at every GC-MRT session. MRI assessments and behavioral tasks will be conducted pre- and post-treatment. All other outcome assessments will be conducted at baseline and at weeks 2, 4, and 8, and 3 months later (3-month follow-up).

**3.3. C.4.a. Primary Outcome Assessment for Target of Attention Allocation:** The primary outcome measure will be defined as % dwell time on threat faces (dwell time on threat faces/dwell time on all faces), derived from eye-tracking data obtained throughout each treatment session. Fixations will be defined as  $\geq 100$  ms of stable fixation within  $1^\circ$  visual angle. For each matrix we will define two Areas of Interest (AOI's), one of the eight disgust facial expressions (i.e., the threat AOI) and one of the eight neutral facial expressions (the neutral AOI). Attention allocation to threat will be measured by computing total dwell time in milliseconds per defined AOI and calculating the proportion of dwell time on the threat AOI relative to total dwell time on both AOI's, thus reflecting gaze allocation to threat stimuli. Percentage of dwell time on threat AOI across the 30 presented matrices for each session will be averaged for a final score of attention allocation to threat per session. As in the pilot study, to derive baseline % dwell time we will average the percentage of dwell time on threat AOI during the first five matrices presented in Session 1, as gaze-contingency learning has been shown to be minimal at this early stage.

**3.3. C.4.b. fMRI Tasks:** Patients will complete MRI twice (pre-treatment and post-treatment) using tasks that have been previously shown to differentiate SAD from control participants. Resting state data will be obtained for 15 minutes prior to task completion.

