### 3.3. C.4.d. Diagnostic and Clinical Rating Assessments

Raters (MD or PhD level) experienced with the assessment of SAD will conduct clinician assessments. Independent evaluators blind to randomization assignment will conduct the primary symptom severity outcome measure (LSAS) and other outcomes. Reliability will be established by joint ratings prior to study initiation and repeated at 6-month intervals during the study to minimize drift.

**MINI International Neuropsychiatric Interview** (MINI, screening only). This structured diagnostic interview will establish DSM-5 diagnoses for eligibility assessment.

**Liebowitz Social Anxiety Scale – Self-Rated** (LSAS-SR, screening only) 24-item self-rated assessment of social anxiety symptom severity, well validated.

**Hamilton Rating Scale for Depression**, 17-item (HRSD, screening and weeks 0,2,4,8, 3-month follow-up)

**Columbia Suicide Severity Scale** (screening and as-needed) will be used for screening and to assess an suicidal ideation occurring during participation.

Outcome measures at weeks 0,2,4,8, 3-month follow-up:

**Liebowitz Social Anxiety Scale – Clinician-Rated** (LSAS) Widely used and well validated 24-item assessment of severity of symptoms of SAD.

**Social Phobia Inventory (SPIN)** – Validated self-rating assessment of severity of symptoms of SAD.

**Quality of Life Enjoyment and Satisfaction Questionnaire (QLESQ)** – Self-rated scale for quality of life.

**Revised Social Anhedonia Scale** – 15-item self-rated scale derived from Chapman Social Anhedonia Scale, with superior discrimination of social anhedonia from social anxiety.

**Post-treatment Debriefing Questionnaire** – This self-rated form will assess the participant's experience of GC-MRT, including treatment acceptability (using a modified version of the **Client Satisfaction**

**Questionnaire**), and awareness of the reward contingency.

**Randomization Method (R61 and R33).** We will use stratified randomization to assign subjects into two randomized groups. Strata will be defined based on baseline medication use (yes/no). Forty subjects will be randomized in the R61 phase to two dosage groups,

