**R61 Go-Nogo Criterion:** Mean % dwell time on threat faces during the last session of the 8-session or 12-session treatment will decrease by more than 7.2 percentage points relative to baseline, corresponding to a medium effect size of Cohen's  $d=0.48$ , based on preliminary data. We have  $>80\%$  power to detect this difference under all scenarios. Clinical significance of cutoff: Based on preliminary data, since % dwell time reduction will partially mediate clinical symptom reduction, this effect corresponds to symptom reduction of  $d = 1.34$ , corresponding to 21.3 points on the LSAS scale. **R61 criterion for selecting dose for the R33:** If only one dosage group passes the Go-Nogo Criterion, that dose will be selected for the R33. If both dosage groups satisfy the Go-Nogo Criterion, we will decide based on the following: If improvement (decrease) in LSAS total score 8 weeks after starting treatment is at least 7 points greater in the 12-session/8-week treatment group than in the 8-session/ 4-week treatment group, we will use the 8-session/12-week treatment in the R33.

**Aim 4: Hypothesis 3:** *Compared to control treatment, GC-MRT will significantly improve symptoms (LSAS) & QoL (Quality of Life Enjoyment & Satisfaction Scale, QLESQ: a) at post-treatment and b) at 3-month follow-up.* As primary analysis, we will use a two-sample t-test for the LSAS change scores at the last session in completer subjects. For the 3-month follow-up, a similar analysis will be performed. Secondary analysis will be similar analyses of the QLESQ, and a mixed effects model of each outcome with change score (relative to baseline) as the outcome, and randomization group, time point, and the baseline score as the predictors. Power Analysis. We assume 10% drop-out in each group. From our preliminary data analysis, expected effect size for reduction in LSAS for completer subjects, compared to controls, will be  $d = 1.35$ . Using a two-sample t-test, with Bonferroni-corrected 0.025 significance level, we will have 99% power to detect this. We do not have preliminary data for the QLESQ; the minimal detectable effect size for the change difference will be  $d=0.74$ , a moderate effect size.

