**Hypothesis 4:** *After GC-MRT, change in % dwell time post-treatment will be significantly associated with improvement in LSAS and QLESQ totals at post-treatment and at 3-month follow-up.* We will calculate Pearson correlation coefficients between % dwell time reduction and LSAS reduction, and, separately, for % dwell time and QLESQ reductions. Power Analysis. From our preliminary data analysis, the expected correlation coefficient for the reduction in % dwell time and reduction in LSAS will be  $r > 0.32$ . With  $n = 80$  subjects and 10% dropout, we will have 80% power to detect a Pearson correlation of  $r = 0.32$  at the 0.05 level.

**Aim 5 (Exploratory):** *To assess whether attention control and reward processing predict symptom change (using same assessment methods as in Aim 3), with fMRI done pre- and post-treatment in a subset ( $n=60$ ).* We will fit regression models, with LSAS change relative to baseline as outcome, and with the baseline predictors listed above as fixed effects, Moderation relationships of treatment effect for the baseline predictors will be explored by including interaction terms with randomization group. We will test the association between change in attention control and reward processing and change in symptoms by Pearson correlation coefficients.

fMRI Data Acquisition: Prior to scanning, patients will practice all tasks and gain familiarity with the scanning environment. Foam pads securing patients in the head coil will limit head movement during data acquisition. The MRI component will last approximately one hour and 15 minutes, using a 3T General Electric MR750 (GE Medical Systems, Waukesha, WI, USA) located in NYSPI, and equipped with a 32 channel receive-only head coil. At the beginning of each session, 15 minutes resting state data will be collected to explore connectivity

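### The secondary mixed model for Hypothesis 3 has no group-by-time term, so it gives one pooled group effect and cannot estimate the post-treatment and 3-month effects separately

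*Combined protocol and SAP*

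**What the plan says.** All of the following is under Aim 4, Hypothesis 3, in Section 3.3. C.5 unless another section is named.

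- The hypothesis covers symptoms (LSAS) and quality of life (QLESQ) at two times: "a) at post-treatment and b) at 3-month follow-up".
- For the primary analysis, "we will use a two-sample t-test for the LSAS change scores at the last session in completer subjects". Then: "For the 3-month follow-up, a similar analysis will be performed". QLESQ gets similar analyses as secondary.
- Also secondary is "a mixed effects model of each outcome with change score (relative to baseline) as the outcome", with "randomization group, time point, and the baseline score as the predictors". The sentence does not say which visits enter, whether time is categorical, or what correlation structure is used.
- The only visit schedule is in the R61 text. Section 3.3. C.4.d lists "Outcome measures at weeks 0,2,4,8, 3-month follow-up", and Section 3.3. C.4 agrees. No R33 schedule is given.
- The opening paragraph of Section 3.3. C.5 justifies mixed models by their ability to handle data missing at random.
- Where the plan wants an interaction it says so. Aim 5 explores moderation "by including interaction terms with randomization group", and the R33 fMRI analyses name group-by-time terms. Where it wants pooling it also says so: Hypothesis 1 is described as pooled over groups and time points, with a separate analysis by time point.

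**The concern.** A model with additive group and time terms has a single group coefficient. That coefficient equals the post-treatment effect and the 3-month effect only if the treatment effect is the same at every visit in the model, which the plan does not state. Hypothesis 3 itself treats the two times as separate claims.

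This matters because of the model's role. The t-tests are specified for completers, or by reference to that specification, and the plan assumes 10% drop-out per group. The mixed model is therefore the natural check on whether the completer results survive when patients with partial data are included. If it estimates an average over visits, agreement or disagreement with a t-test at one visit is hard to interpret: a difference could come from missing data or simply from pooling over time.

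**Working it through.** **Inputs from the plan.** 80 patients (Hypothesis 4 power statement), 10% drop-out, Bonferroni level 0.025, expected LSAS effect d = 1.35, minimal detectable QLESQ effect d = 0.74.

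**Assumptions.** 1:1 allocation, so 36 completers per arm (40 × 0.9); two-sided test; equal SD of change at each visit; correlation between visits r = 0.4 to 0.8; complete data at the visits modelled. The documents give no correlation for LSAS or QLESQ change and no correlation structure for this model.

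**1. The plan's own figures.** Two-sample t-test, 36 per arm, 70 degrees of freedom, level 0.025:

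- Power at d = 1.35 is 99.96% by noncentral t (plan: 99%).
- The d detectable with 80% power is 0.740 (plan: 0.74).

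Both reproduce. They belong to the t-tests, not to the mixed model.

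**2. What the additive model estimates.** With correlation matrix R over the visits, the group coefficient is the sum of w × d over visits, with weights w = R⁻¹1 / (1′R⁻¹1) and standard error √(v × 2/36), where v = 1/(1′R⁻¹1). Approximate power is Φ(coefficient/SE − 2.241).

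**3. Only post-treatment and 3 months enter.** Each visit has weight 0.5 and v = (1 + r)/2. Take d = 1.35 and then 0:

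- Coefficient = (1.35 + 0)/2 = 0.675.
- r = 0.4: SE = √(1.4/36) = 0.197; 0.675/0.197 − 2.241 = 1.18; probability of significance 88%.
- r = 0.8: SE = √(1.8/36) = 0.224; 0.675/0.224 − 2.241 = 0.78; probability of significance 78%.

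**4. The R61 visits carry over (weeks 2, 4, 8 and 3 months), 8-week course.** Section 3.3. C.3 gives 12 sessions over 8 weeks, with the first 8 in 4 weeks. Sessions delivered by weeks 2, 4 and 8 are then 4, 8 and 12 of 12. If the effect builds in proportion and is held to 3 months, the pattern is 0.45, 0.90, 1.35, 1.35.

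- Compound symmetry: weights 0.25 each; coefficient = 4.05/4 = 1.01.
- AR(1), r = 0.4: weights 0.3125, 0.1875, 0.1875, 0.3125; coefficient = 0.3125 × 1.80 + 0.1875 × 2.25 = 0.98.
- AR(1), r = 0.8: weights 0.417, 0.083, 0.083, 0.417; coefficient = 0.417 × 1.80 + 0.083 × 2.25 = 0.94.

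So the coefficient is 0.94–1.01, or 69–75% of 1.35. Power at 0.025 is still about 99% or more in every case. The AR(1) cases treat the four visits as equally spaced, which they are not.

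**5. Simulation with and without the interaction.** 300 runs, 36 per arm, compound symmetry with r = 0.6, effects 0.45, 0.90, 1.35 and 0 at the four visits:

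| Model | Estimate | Rejects at 0.025 |
|---|---|---|
| Additive, group coefficient | 0.65 | 88% |
| Group × time, week 8 | 1.32 | 99.7% |
| Group × time, 3 months | −0.02 | 3% |

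The interaction model separates the two effects; the additive model reports one number that is neither.

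**The case against.** The strongest reply is that both claims already have their own test. The t-tests at the last session and at 3 months are time-specific, and the mixed model is secondary. This stands. A reader might infer that Hypothesis 3 goes untested or loses its stated power; the documents do not support that.

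A reader might also infer that a significant pooled coefficient would be taken as proof of a lasting effect. Nothing in the plan lets that coefficient decide the 3-month claim. The 78–88% above is the chance that a pooled test detects a real average effect; it is not a false-positive rate for the 3-month claim.

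Third, the visits are not known. Weeks 2, 4, 8 and 3 months come from the R61 text. If only post-treatment and 3 months enter and the effect is held at 1.35, the coefficient is 1.35 and nothing is diluted. So the understatement is conditional on the visit list. It also depends on how the effect builds: scaling by calendar week (0.34, 0.68, 1.35, 1.35) would give 0.87–0.93, but that does not match the session schedule in Section 3.3. C.3. Section 3.3. C.5 describes the longer course differently (8 sessions, 12 weeks), and those passages need to be reconciled.

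Last, the predictor list may be shorthand, since the sentence omits other details too. The interactions named elsewhere make an omission more likely but do not prove it. Either way, an analyst following the text would fit the additive model.

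**Conclusion.** The point holds as a specification gap in a secondary analysis. As written, the Hypothesis 3 mixed model cannot estimate the post-treatment and 3-month effects separately, whichever visits enter and whatever the correlation. That follows from the predictor list alone.

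Its numerical size is illustrative only. With two visits and an effect that vanishes by 3 months, the model reports 0.675 where the true values are 1.35 and 0. With the R61 visits and a held effect, it reports about 0.94–1.01 where both target values are 1.35. These figures rest on the assumed effect patterns, equal SDs and r = 0.4–0.8.

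It would be wrong to conclude that the LSAS comparison is underpowered or that the primary analysis is affected. What is lost is a usable check, with partial data included, on the two results that Hypothesis 3 is about.

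**What to change.** Add randomization group × categorical time to the Hypothesis 3 mixed model. Prespecify two model-based group differences, at post-treatment (claim a) and at 3 months (claim b), for LSAS and for QLESQ, using all randomised patients with post-baseline data. State which R33 visits enter, which visit counts as post-treatment for the course selected from R61, and the within-patient correlation structure.

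This changes a few lines of SAP text and needs no new data. It uses a few degrees of freedom, and the intervals are wider than for a pooled effect. With complete data the SE of a visit-specific difference is about √(2/36) = 0.236 SD. For the pooled effect over two visits it is 0.197 (r = 0.4) to 0.224 (r = 0.8), so the visit-specific intervals are about 5–20% wider. With four visits pooled, they are about 8–51% wider, depending on correlation and structure. Since 0.236 is also the SE behind the plan's own t-test power figures, precision does not fall below what the plan already accepts.

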### 3.3. C. Research Design and Methods: R61 Phase.

**3.3. C.1. Overview.** The R61 Phase is designed to clarify engagement of the attention allocation target, to optimize dosage of GC-MRT (RCT comparing 8 vs. 12 sessions), and to explore whether the treatment engages two processes influencing attention allocation: disengagement from threat, and social reward.

**3.3. C.2. R61 Method: Patients:** The goal is to enroll a sample with clinically significant SAD, using few exclusion criteria to maximize generalizability. Patients will be obtained by clinical referral and recruitment notices posted online and locally. Forty adults age 18-60 with clinically significant SAD, as assessed by MINI structured interview and self-rated Liebowitz Social Anxiety Scale (LSAS-SR) total  $\geq 50$ , will enter the study after psychiatric clinical evaluation, including and Hamilton Rating Scale for Depression (HRSD). The LSAS cutoff score was chosen for optimal balance between diagnostic specificity and sensitivity for SAD. Key exclusion criteria will be at least moderately severe depression (HDRS 17-item score  $>20$ ), indicating greater need for non-experimental treatment; substance use disorder in the past 30 days (other than nicotine, or mild alcohol or cannabis abuse); bipolar or psychotic disorders; acute suicidal ideation (assessed by Columbia Suicide Severity Rating scale, CSSR); other unstable psychiatric, neurological, or medical conditions that could interfere with study participation or interpretation of outcomes; contraindication to MRI. (see Human Subjects for details).

[figure not shown]
The self-rated version of the LSAS will be used only at screening for eligibility assessment. The clinician-rated LSAS will be the primary outcome measure, assessed at baseline, during treatment, and post-treatment. Using the self-rated LSAS at screening avoids the bias that reportedly can occur when the primary outcome measure is the basis for an entry cutoff criterion, as raters could feel pressured to maximize baseline scores to meet the cutoff, thus distorting outcomes.

**3.3. C.3 R61 Intervention:** Patients will be randomized to 8 biweekly sessions of GC-MRT over 4 weeks vs. 12 sessions of GC-MRT over 8 weeks (8 biweekly, then 4 weekly), using GC-MRT as described above in the preliminary study, but without a control treatment – all R61 patients will receive active GC-MRT.

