Whole-brain 2X2 voxel-wise Analysis of Variance (ANOVA) will be conducted to evaluate main effects of Time (pre- and post- treatment), Stimuli type (match faces and match shapes), and Time by Emotion interactions for only angry faces at the R61 phase for each dose group. For the R33 phase, whole-brain 2X2X2 ANOVA will be conducted to evaluate main effects of Group (active and control), Time (pre- and post-treatment), and Stimuli type (match faces and match shapes), and Group by Time by Stimuli type interactions for only angry faces. A stringent threshold for significance will be set at  $p < 0.05$ , corrected for multiple comparisons across the entire brain using a FWE with a cluster size of at least 10 contiguous voxels. Significant main effects and interactions will be tested by post hoc t-tests to clarify the direction of effects.

**Reward Task fMRI:** During individual-level analyses, functional activation maps of the reward task will be computed by regressing each voxel's fMRI response time course onto an ideal response function consisting of a canonical hemodynamic response function convolved with the time-series of each response type of the entire duration of anticipation and outcome phases of the task. In addition, six movement parameters obtained during realignment were included in the model as regressors to account for motion-related effects in BOLD signal.

A whole-brain voxel-wise two-way t-test model will be conducted with two time points (pre-, post-treatment) in the R61 phase for each dose group. It will be applied separately for the anticipatory and outcome phases of the task, and each outcome will be modeled against an implicit baseline (the anticipatory phase models only 'potential win' trials and the outcome phase models only successful 'potential win' trials). For the R33 phase, whole-brain 2X2 ANOVA will be conducted to evaluate main effects of Group (active and control), and Time (pre- and post- treatment), and Group by Time interactions. Significant clusters will be further evaluated by extracting subject- and condition-specific signal intensity coefficients to evaluate simple effects.

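### Hypothesis 4 does not name its analysis population: its 80% power needs about 72 completers, its wording implies about 36, and a pooled correlation would not be adjusted for arm

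*Combined protocol and SAP*

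**What the plan says.** In section 3.3. C.5, under Aim 4, Hypothesis 4 reads "After GC-MRT, change in % dwell time post-treatment will be significantly associated with improvement in LSAS and QLESQ totals", at post-treatment and at the 3-month follow-up. The analysis is given as "We will calculate Pearson correlation coefficients between % dwell time reduction and LSAS reduction", with a separate correlation for QLESQ. No analysis set is named and randomization group is not mentioned.

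The power paragraph expects a correlation above 0.32 for dwell time and LSAS. Starting from n = 80, it says "subjects and 10% dropout, we will have 80% power to detect a Pearson correlation of" 0.32 at the 0.05 level.

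Elsewhere in the same section, randomization group is in the models. The secondary mixed model for Hypothesis 3 takes change from baseline as the outcome "and randomization group, time point, and the baseline score as the predictors". For Aim 5, "Moderation relationships of treatment effect for the baseline predictors will be explored by including interaction terms with randomization group".

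**The concern.** The opening words of the hypothesis point to treated patients, while the sample size appears to count treated and control patients together. The two readings exclude each other, and each has a defect.

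- **GC-MRT arm only.** This matches the wording, but the sample is about half of the one used for the power figure.
- **Both arms pooled.** This matches the sample size. But if treatment lowers both dwell time on threat and LSAS, patients from the two arms form two separated clouds, and a plain correlation is positive even when the two changes are unrelated among patients on the same treatment.

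Hypothesis 4 is the test that links the attention target to clinical benefit. As written, it is either underpowered at the lower bound of the expected correlation, or it can reach significance through the arm difference alone. Leaving the population open also allows it to be chosen after the data are seen.

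**Working it through.** **Inputs from the plan.** n = 80, 10% dropout, r = 0.32, alpha 0.05, stated power 80% (Hypothesis 4). Between-arm LSAS effect d = 1.35, 10% dropout per group, alpha 0.025, and a detectable d of 0.74 for QLESQ (Hypothesis 3). Pre-post dwell-time effect d = 0.68 (Hypothesis 1) and 0.48 (go/no-go criterion).

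**Assumptions.** Two-sided tests; 1:1 allocation in the R33; a range of between-arm dwell-time effects, because the documents give none.

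**1. The plan's figure.** Completers: 80 × 0.90 = 72. By Fisher's z, power = Φ(atanh(r)·√(n − 3) − 1.960). With atanh(0.32) = 0.3317:

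- n = 72: 0.3317 × √69 = 2.755; 2.755 − 1.960 = 0.795; power 78.7%. A noncentral-t calculation gives 80.7% and simulation 79.4%. The stated 80% is reproduced for 72 completers.

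**2. Who the 80 are.** Aim 4 compares GC-MRT with a control. R61 has no control, since "all R61 patients will receive active GC-MRT" (3.3. C.3), and the R33 imaging analyses compare active with control groups. For Hypothesis 3 the plan says "We do not have preliminary data for the QLESQ; the minimal detectable effect size for the change difference will be" 0.74. A two-sample t-test at alpha 0.025 with 80% power has these detectable effects:

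| Completers per arm | Detectable d |
|---|---|
| 35 + 35 | 0.751 |
| 36 + 36 | 0.740 |
| 37 + 37 | 0.730 |
| 48 + 24 | 0.785 |

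Thirty-six per arm (40 × 0.90) fits, which makes 80 the total of both R33 arms. This is an inference. Forty R61 patients plus 40 R33 GC-MRT patients would also total 80, but no text pools the phases.

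**3. GC-MRT arm only, n = 36.**

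- r = 0.32: 0.3317 × √33 = 1.905; 1.905 − 1.960 = −0.055; power 47.8% (simulation 48.8%).
- r = 0.40: power 68%. r = 0.45: power 80%.
- Detectable r = tanh((1.960 + 0.842)/√33) = tanh(0.488) = 0.45. For n = 72 the same formula gives tanh(2.802/√69) = 0.325.

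**4. Both arms pooled, n = 72.** With within-arm correlation ρ and between-arm standardised differences dx (dwell) and dy (LSAS), the pooled correlation under 1:1 allocation is (ρ + dx·dy/4)/√((1 + dx²/4)(1 + dy²/4)). With ρ = 0 and dy = 1.35:

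- dx = 0.48: 0.162/√(1.0576 × 1.4556) = 0.13
- dx = 0.68: 0.2295/√(1.1156 × 1.4556) = 0.18

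Rejection rates at 0.05 in 40,000 simulated trials of 36 + 36 with ρ = 0:

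| Assumed between-arm dwell d | Pooled Pearson | Arm-adjusted |
|---|---|---|
| 0 | 5% | about 5% |
| 0.20 | 8% | about 5% |
| 0.34 | 12% | about 5% |
| 0.48 | 19% | about 5% |
| 0.68 | 34% | about 5% |
| 1.0 | 58% | about 5% |

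Solving the same formula for ρ, a pooled correlation of 0.32 would correspond to a within-arm correlation of only 0.24 (dx = 0.48) or 0.18 (dx = 0.68).

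**5. What arm adjustment costs.** One covariate removes one degree of freedom: detectable partial r = tanh(2.802/√68) = 0.33. Power at r = 0.32 in both arms is 78% by Fisher's z and 79% by simulation. If r is 0.32 in the GC-MRT arm but 0.16 or 0 among controls, simulated power falls to 53% or 27%. The GC-MRT-only test has 49% in the same simulation.

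**The case against.** **The R33 size is inferred.** The text available for review does not state the R33 sample size or allocation ratio, and the 0.74 figure carries no stated power. At alpha 0.05, 30 per arm would fit it too, and at alpha 0.025 so would a mild imbalance such as 39 + 33. This stands as a caution. But 30 per arm is 60 completers, which is 25% dropout from 80, not 10%. With 33 to 39 GC-MRT completers, power at r = 0.32 is Φ(0.3317·√30 − 1.960) to Φ(0.3317·√36 − 1.960), i.e. 44% to 51%, so the conclusion does not change.

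**At most one defect can apply.** True: if the plan means both arms, the 48% never arises. But then the missing arm adjustment does.

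**The rejection rates are hypothetical.** They rest on assumed between-arm dwell effects and on zero within-arm association, whereas the plan expects dwell reduction to mediate part of the symptom benefit. With a dwell effect above 0 the pooled correlation is truly non-zero, so these rejections are not false positives for the pooled quantity. That is correct. They show that the pooled correlation answers a different question and cannot separate an association within treated patients from treatment moving both measures independently.

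**The plan uses plain correlations elsewhere.** Aims 3 and 5 do so for change against change, so Hypothesis 4 is not out of line with them. But those aims are exploratory, and the parallel does not remove the problem in a powered hypothesis.

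**Conclusion.** The concern holds. The power arithmetic is right for 72 completers, but neither the population nor the handling of arm is stated, and the wording does not match the sample size. Restricted to GC-MRT patients, power at r = 0.32 is about 48% rather than 80%. Since the plan expects a correlation above 0.32, that is the power at its lower bound. Pooled and unadjusted, the test can be significant with no association within arms, by an amount that depends on a between-arm dwell effect the documents do not give; if that effect is zero there is no inflation. These figures assume 1:1 allocation and that the 80 are both R33 arms. The point should be fixed before the R33 analysis.

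**What to change.** Add one sentence naming the Hypothesis 4 analysis population, then follow one of two routes.

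- **Both arms.** Regress LSAS change and, separately, QLESQ change on dwell-time change with randomization group as a covariate (or use the partial correlation). Report the within-GC-MRT estimate with its confidence interval. State that the power (78% to 79%, detectable partial r about 0.33) assumes a correlation of about 0.32 in controls as well as in GC-MRT patients.
- **GC-MRT patients only, as the hypothesis is worded.** Keep the Pearson correlation and restate the detectable value as about 0.45 with 36 completers, with power of about 48% at r = 0.32.

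Neither route needs more patients or assessments. The first is no longer specific to GC-MRT patients and has less power than the second if controls show no association (27% against 49%). The second costs a less favourable power statement.
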